## **AIM 2**

*Aim 2* will involve adaptation of the iOTA intervention using the Stirman adaptation framework, including modification of contextual, content and training aspects of the treatment based on qualitative data collected using the I-Corps methods. These might include adaptations to the treatment manual, in-person visit structure, and SMS text messaging. Once adaptations have been completed, they will be tested for feasibility by members of the focus groups queried in Aim 1 via semi-structured interview. Final adaptations will be made based on interview data.

**Study Participants** Individuals who participated in Aim 1 focus groups will be queried with individual semi-structured interviews to obtain feedback on treatment adaptations.

### **Aim 2 Study Procedures**

**iOTA adaptation Procedures:** We will work with the parent WfY study intervention team to make adaptations to the existing intervention manual and text messaging protocol. We will then use a process for message and technology testing that follows the process used for the adaptation of the parent iOTA program, which uses personalized daily and weekly feedback via text messaging. Text message adaptations for the proposed project will be based on those used in previous iOTA studies aimed at low-income people and racial minorities and those used in the current St. Louis study in the workplace. Before deployment, existing libraries of text messages will be tested for usability and cultural appropriateness among members of our target

population of eSMI patients. We will conduct key informant interviews using the I-Corps methodology following this testing and adapt the messages and risk assessment platform as needed based on this information.

**Key Informant Interview Procedures:** Using a standardized interview guide developed using I-Corps methods, we will conduct semi-structured, in-person key informant interviews with 1-2 members from each focus group at each study site to obtain impressions about adaptations made based on focus group results. Interviewing will be curtailed when saturation occurs (i.e., when the same themes repeatedly emerge). We will focus in particular on clients, caregivers and case managers, whose buy-in, participation, and ongoing support will be critical for our intervention at the level of the CMHC.

**Data Management and Analytic Plan:** Interviews will be digitally recorded and transcribed verbatim. Transcripts will be used in conjunction with notes taken during the interview, and will be analyzed using NVivo software. Themes will be grouped into categories informed by the overall aims of the interviews, including attitudes toward the adapted iOTA intervention, feasibility of interventions in specific age/race/ethnic groups, and organizational barriers and facilitators to health promotion in the CMHC setting. Experienced raters will use the tree to code transcripts using NVivo software for coding and analysis. Data will be analyzed using standard content analysis strategies listed in Aim 1.

### **AIM 3**

In this aim we will work with BJC BH and SFBHN to implement and evaluate the adapted iOTA-eSMI intervention that provides support for behavior change to increase physical activity and modify diet, in order to achieve clinically significant weight loss and/or prevent obesity, thereby reducing diabetes and cardiovascular disease risk in eSMI. For the proposed iOTA testing, all otherwise eligible eSMI clients who have experienced  $\geq 7\%$  increase in weight in the past 2 years and/or are currently overweight (BMI 25-29.9) or early class I obesity (BMI 30-32.49) by BMI will be offered participation in the adapted iOTA. Our proposed pilot study aims to assess feasibility, acceptability, tolerability, and target engagement and will explore one primary hypothesis: participants in the intervention group will show favorable change in body weight compared to clients in the Health Education Control group. Secondary analyses will assess iOTA effects BMI and on RDoC domains relevant to needed psychophysical skills and self-efficacy, exploring the relationship between weight change and target engagement. Feasibility, engagement and implementation challenges will be characterized, measured by i) enrollment & retention, ii) obesity intervention acceptability, iii) text response rates, iv) visit adherence v) client expectations, vi) fidelity and vii) CMHC staff-rated acceptability, appropriateness and burden. To achieve these goals, we will conduct a randomized controlled pilot study in 60 eSMI patients ages 18-45. Participants will be randomized 2:1 to 24 weeks in the Psych iOTA Program or in the Health Education Control program. Both intervention groups will have monthly in-person visits with a health coach. The iOTA group will receive daily text messages specific to health goals set during the in-person visits, and will receive treatment content that incorporates empirically supported approaches to increasing self-efficacy and psychophysical awareness. The Health Education Control group will receive education based on the Stanford health care self-management program developed by Kate Lorig and colleagues and modified to be similar to the iOTA intervention in number and length of visits. We will also obtain acceptability, appropriateness and feasibility feedback from case managers and clients on benefits, barriers, and suggested improvements to the SMS portion of the intervention during monthly in-person health coaching visits.

***Study Participants*** Aim 3 will include a randomized 24-week pilot study of the adapted intervention, followed by 12 weeks of text messaging intervention alone in 60 participants (30 at each study site). Participants will be CMHC clients aged 18-45 with eSMI receiving mental health services at each clinical site, and will be randomized 2:1, iOTA-eSMI intervention: health education control. Groups will be balanced to reflect the age, gender, racial and ethnic distribution of the client-base at each site. Targeted group size for this pilot study will permit exploration of treatment group interactions with age and with racial/ethnic differences. The study manager, under the supervision of the study statistician, will maintain control of the randomization matrix to ensure unbiased group assignment during the randomization process. Although this is not a blinded study, the PI's and health coaches will not be involved in any part of the randomization to further ensure an unbiased process.

***Inclusion criteria:*** i) aged 18-45 years, ii) "at-risk" weight defined as  $>7\%$  weight gain in the prior 2 years, overweight (BMI 25-29.9) OR class I obesity (BMI 30-32.49) iii) SMI diagnosis with  $<5$  years treatment,

iv) receiving case management services in one of the two CMHC study sites v) University of California, San Diego Brief Assessment of Capacity to Consent (UBACC) score  $> 14$  vi) not taking weight loss medications or participating in another behavioral weight loss intervention, vii) mild to moderate psychiatric symptom severity as measured by the Clinical Global Impression – Severity scale viii) willing and able to provide written informed consent.

**Exclusion criteria:** i) taking weight loss medications or participating in another behavioral weight loss intervention, ii) documented diagnosis of diabetes and/or treatment with an antidiabetes agent (diagnoses of hypertension and hyperlipidemia acceptable), iii) UBACC score  $\leq 14$ , iv) acute suicidality at time of screening, v) unwilling or unable to provide written informed consent.

#### **Randomization of participants:**

Participants will be randomized 2:1 to 24 weeks in the Psych iOTA Program or in the Health Education Control program. Both intervention groups will have monthly in-person, zoom, or telephone visits (lasting approximately 1 hour (Baseline and final visit lasting ~ 2 hours) with a health coach. Documentation of the screening and monthly visit assessments will be directly entered into a secure REDcap database by the Health Coaches at each site. Each site will have weight scales for documenting of weight changes.

The iOTA group will receive daily text messages specific to health goals set during the in-person visits, and will receive treatment content that incorporates empirically supported approaches to increasing self-efficacy and psychophysical awareness.

The Health Education Control group will receive education based on the Stanford health care self-management program developed by Kate Lorig and colleagues and modified to be similar to the iOTA intervention in number and length of visits. We will also obtain acceptability, appropriateness and feasibility feedback from case managers and clients on benefits, barriers, and suggested improvements to the SMS portion of the intervention during monthly sessions with PIs and staff at the Healthy Mind Lab located in the Taylor Avenue Building on the Washington University Medical Campus and at the South Florida Behavioral Health Network facilitates at our associated two Florida study sites (Fellowship House and Guidance Care Center) and at the Independence Center Organization in St. Louis, MO.

Participants unable to attend visits in person will have the option of attending study visits remotely by phone or by using a Washington University-approved video conferencing platform (Skype or Zoom) and digital links to study assessments in REDCap. For potential participants who have computer access and capability, study visits may be conducted via video conferencing. The health coach will use a secure, web-based, HIPAA-compliant, conferencing platform that employs encryption of video and audio content. Potential participants would receive an email or text message with a unique and secure link to join the video session by computer or mobile device.

#### **Participant Enrollment:**

We will recruit 60 adult probands from MO and FL CMHCs with SMI.

#### **Recruitment and Screening Procedures:**

Fliers will be distributed to community mental health centers and local medical professionals in order to recruit participants. These handouts list the inclusion criteria, benefits of being in the study, and contact information for questions or to enroll. In addition to referrals from providers, study staff will review EPIC patient lists to identify potential participants. Potential participants will then be contacted to introduce them to the study and complete an initial screening for eligibility.

During the initial screening phase, a member of the research team will obtain verbal consent to conduct an IRB approved phone screen with individuals who express interest in participating. There will be questions about a person's medical and mental health history. After completion, a member of the research team will examine and determine whether inclusion criteria are met and contact the individual. No study procedures will begin prior to obtaining informed consent.

### **Informed Consent Process:**

The research team will obtain informed consent from all subjects who participate in the study. The study procedures will be explained in writing and/or orally to the subject by a member of the research team. After all questions have been answered and the risks and benefits of participation in the study have been described, informed consent will be obtained on an informed consent form approved by the WUSM IRB and Human Research Protection Office. The research team will confirm that the subject verbalizes understanding of the study and study-related procedures and be given the opportunity to ask questions prior to obtaining the research participant's signature. The objectives of the project, all of the requirements for participation, the efforts made to protect the private health information and confidentiality of the participant, and any possible discomforts and risks will be clearly explained to the subjects orally and in writing in lay terms which they are able to comprehend.

A member of the research team will witness the subject sign and date the informed consent form as part of the informed consent process and signs as the person obtaining informed consent. Adult participants will be asked to provide informed consent for their own participation. Potential adult participants that have limited decision making capacity will be included in this study, and their legal guardians or legally authorized representatives will be consented and will provide written informed consent for them to participate in the study. Informed consent is an ongoing process. All study related procedures will be explained at each visit and participants will be reminded that participation in research is voluntary and they may refuse to participate or withdraw from the study at any time without penalty or loss of benefits to which they would otherwise be entitled. Should a change be made to the consent document at any time during the subject's participation, the subject and/or legally authorized representatives will be re-consented.

The consent process may take place by phone for participants who have barriers to in-person participation. For potential participants who have computer access and capability, the formal study consent process will be conducted using a REDCap-based electronic consent form. The consent form has been developed in REDCap, a secure, web-based, HIPAA-compliant, data collection platform with a user management system allowing the principal investigator to grant and control varying levels of access to study staff. Potential participants will receive an encrypted email with a unique link to review the informed consent form online. After the research team explains the study and answers any question, the potential participants can electronically fill in an "Agree" button, followed by their electronic signature. Upon completion of the consent, participants are presented with the option to download a copy of the executed form. The research team will also send a [secure] e-mail copy of the executed form to the participant. E-consent versioning will be managed using the e-consent Framework in Redcap. Within the e-consent survey options, we have designated the e-consent version number in this application as e-consent version 1. The PDF's of completed responses will have the timestamp, participant name, and e-consent version number inserted in the footer. Future versions of the e-consent will be created by making a copy of the Redcap form and revising it. The old version would be deactivated upon receiving IRB approval for the new version.

If a participant does not have access to a computer at the time of consent potential participants will be provided with a copy of the informed consent form (via mail or email). Once the potential participant has had time to look over the consent form, a study team member will talk with the participant by phone to review the study information and answer any questions. If they choose to continue their participation, they will be asked to sign the consent and return to us either by mail or scanned and emailed or faxed or to verbally agree to take part in the study, which will be recorded in the study record. For any consent document returned, we will instruct participants to keep a copy for themselves.

### **Detailed Study Procedures:**

*Literacy & facility with mobile technology:* Each participant will be administered the Rapid Estimate of Adult Literacy in Medicine-Short Form or REALM-SF to estimate literacy and the University of California, San Diego Brief Assessment of Capacity to Consent or UBACC to establish understanding of the study and active treatment. The accessibility of and ability to use mobile devices is necessary for participation in this study.

Thus, prior to randomization, all participants will undergo one week of text messaging to ensure that they are able to receive and appropriately respond to text messages.

**Rationale for study length of 24 weeks:** In the MEAC study, the PI's demonstrated rapid onset weight gain within 12 weeks of initial antipsychotic exposure. Although weight gain, particularly that associated with medications, can be rapid, it is generally well accepted that meaningful weight loss efforts may take longer than 12 weeks. We plan for a fully powered future study with an active treatment phase that is 6 months in duration, similar to currently running Phase 3 clinical trials (cite Alkermes). Published weight loss intervention studies in mentally ill youth and adults of 4 months in duration show separation from control groups. For the proposed study, our primary goal is to establish feasibility, tolerability and target engagement during active treatment, as well as to evaluate engagement and outcomes following a text-only 12-week extension.

**iOTA intervention:** The individual-level interactive obesity treatment approach (iOTA) intervention is based on assessment of individual behavior risks, collaborative goal-setting with a health coach, and use of an interactive text system to provide ongoing support and self-monitoring of behavior change goals. The SMS intervention is programmed to "touch" participants an average of five days per week. The SMS system prompts participants to report their weight and their progress on achieving their goals on a "check-in" day each week, and sends immediate, tailored feedback about their progress. If a participant is making progress on their goal, the SMS system suggests a change to the participant's goal in between health coaching sessions. In addition, the system sends weekly and monthly tips customized to the goals the participant selected. The iOTA intervention has been adapted for use in mentally ill populations, including monthly in-person visits and weekly telephone check-ins as needed depending on level of engagement with the SMS messaging, monitored by the health coaches remotely via a web portal. Monthly in-person visits consist of assessing current health behaviors, working collaboratively with the client to identify desired behavior changes, then using a list of 19 goals including stepped level of difficulty based on participant's current behaviors, the client and health coach collaboratively select up to three goals for the next month. These goals have prescribed SMS messaging tailored to level of difficulty to support the participant on a daily basis with health behavior change.

**Health Education Control:** A control condition that matches for group setting, time, and attention is necessary to minimize the chance that study findings might be attributable to non-specific differences in conditions rather than the active ingredients of the adapted iOTA intervention. Health Education is based on the Stanford health care self-management program developed by Kate Lorig and colleagues. Health Education improves chronic disease management, but it does not teach self-efficacy or psychophysical awareness, and does not involve specific empirically supported psychotherapeutic techniques to help with weight management. It matches iOTA in time and number of sessions. Participants randomized to the control condition will receive monthly in-person health coaching visits and a weekly SMS general "Health Tip" message. Visits will be structured according to current US Preventive Services Task Force recommendations to counsel participants on energy balance, physical activity and nutrition. The Health Coach will use educational materials developed for the iOTA-SMI adaptation for health education groups, which includes information from [www.MyPlate.gov](http://www.MyPlate.gov) and from the Be Fit Be Well program. Health education control group participants will not be engaged in formal goal setting.

**Ensuring Rigor & Reproducibility:** Behavioral intervention treatment fidelity is determined by structured, direct observation of individuals carrying out the behavioral intervention, evaluating for evidence of 1) adherence to the treatment protocol and 2) competence in the treatment delivery. The demonstration of treatment fidelity is critical to the development of a valid behavioral intervention, such that the intervention cannot be tested for efficacy in a randomized clinical trial, nor can said intervention be considered evidence-based until this critical step is accomplished. Therefore, a primary goal of the proposed project is to demonstrate treatment fidelity of the iOTA and Health Education Control in-person health coaching visits. This will be accomplished by audio-recording monthly in-person sessions, which will be reviewed by the PIs and discussed during weekly study teleconferences. Health Coaches will self-monitor treatment fidelity at each visit using an established Treatment Fidelity and Competence Rating Scale.

## **Study Assessments Completed at Baseline Only**

**UC San Diego Brief Assessment of Capacity to Consent (UBACC):** This is a 10-item scale developed to determine whether potential research participants are capable of providing informed consent. Questions focus on understanding the purpose of the research protocol, safety and ability to withdraw consent.

**Credibility and Expectations for Improvement (CEI):** Participants will be asked to rank their expectations about the intervention and how much they believe it is reasonable and will be useful on a likert scale. Both case managers and clients will be asked to complete this questionnaire prior to study initiation.

### **Study Assessments Completed at Baseline and Endpoint**

**The Health Status/Knowledge/Behaviors/Attitudes Questionnaire** will be completed at Baseline and Endpoint, and includes:

**Rapid Eating Assessment for Patients -Short Form (REAPS):** This is a very quick assessment of daily diet quality and eating behaviors that the health coach will use to assess for any eating areas in need of dietary counseling and education.

**International Physical Activity Questionnaire - Short Form (IPAQ-SF):** This is a 7-item questionnaire that measures intensity of physical activity in the last 7 days, including time spent sitting.

**Ten Item Personality Inventory (TIPI):** This is a brief, 10-item measure of the Big-Five personality dimensions.

**Questionnaire on Eating and Weight Patterns-DSM 5 (QEWP-5):** The Questionnaire on Eating and Weight Patterns (QEWP) is a 26-question self-report screening tool that has been developed for use in research and clinical settings to identify persons who may have binge eating disorder or bulimia nervosa, and has been updated to conform to DSM-5 diagnostic criteria for BED (QEWP-5).

**Activity Tracking:** Participants will be given a Fitbit Flex to be worn for 1 week prior to study visit 1 and endpoint visits. Data will be downloaded by the health coach upon return of the device.

### **Digital Behavioral Assessment Completed by the Participant at Each Study Visit**

At each visit, participants will fill out a digital assessment battery that self-scores and provides recommendations for treatment focus in the visit.

**Patient Health Questionnaire (PHQ-9):** This 9-item scale measures symptoms of depression on a scale of 0 (not at all) to 3 (nearly every day). Scores >10 is consistent with moderate depressive symptoms and will prompt the health coach to consider use of emotion regulation techniques to promote emotion regulation.

**Self-Efficacy for Mental Health.** This is a 6-item visual analogue scale from 1-10 (1 = not at all confident, 10 = very confident) that assesses perceived control over emotional states and ability to cope with stress. A mean score >15 will prompt consideration of emotion regulation or distress tolerance materials.

**Loss of Control over Eating Scales (LOCES).** The LOCES is a 7-item scale that measures behavioral, cognitive/dissociative, and positive/euphoric aspects of loss-of-control eating on a scale of 1 (never) to 5 (very often). Scores > 25 will prompt the health coach to consider use of dialectic behavior therapy strategies to promote self-regulation to prevent binge and loss of control eating (mindfulness, distress tolerance).

**Psychophysical Awareness & Skills Scale (PASS).** This composite measure draws from RDoC (NIH Research Domain Criteria) domains of cognitive systems and social processes, and includes 10 items that assess cognitive control, self-determination and interoceptive awareness on a likert scale. A mean score <4 will prompt the health coach to utilize materials related to improving awareness of hunger and satiety cues.

**Self-Efficacy (Diet and Exercise).** This scale consists of 32 items (20 nutrition-based, 12 activity-based) and assesses a participant's current eating and exercise behaviors and knowledge on a likert scale. A mean score < 4 on either subscale will prompt the health coach to access energy balance and self-efficacy treatment content.

**UCLA Loneliness Scale (Version 3).** A 20-item scale designed to measure one's subjective feelings of loneliness as well as feelings of social isolation. Participants rate each item on a scale from 1 (Never) to 4 (Often). Higher scores are correlated with poorer social functioning in friendships and romantic relationships. Scores >40 will prompt use of interpersonal effectiveness materials in coaching sessions.

**Multidimensional Scale of Perceived Social Support.** This 12-item scale is designed to measure perceived social support from three sources: Family, Friends, and a Significant Other. Scores < 3 will prompt use of interpersonal effectiveness materials in coaching sessions (identifying relationships that support health behavior change, shoring up interpersonal effectiveness skills).

**Clinical Global Impression Scale.** The CGI was developed for use in NIMH-sponsored clinical trials to provide a brief, stand-alone clinical assessment of the patient's global functioning, taking into account the patient's history, psychosocial circumstances, symptoms, behavior, and the impact of the symptoms on ability to function.

**Medication Reconciliation & Compliance:** Our group has developed a medication log and reconciliation form to track medication compliance and changes during study participation. Participants will be asked at each in-person health coaching visit to update their medication list, which will then be reconciled with the case manager, physician and pharmacy.

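### The mental-health self-efficacy trigger lies above the top of its scale and points the wrong way

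*Protocol*

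**What the plan says.** The Protocol section on the digital behavioral assessment, completed by the participant at each study visit, describes a battery that scores itself and suggests where the coach should focus. For Self-Efficacy for Mental Health it says: "This is a 6-item visual analogue scale from 1-10 (1 = not at all confident, 10 = very confident"). The construct is perceived control over emotional states and the ability to handle stress. The trigger follows: "A mean score >15 will prompt consideration of emotion regulation or distress tolerance materials".

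Neighbouring scales have their own triggers. Where a high score is bad, the prompt fires on a high score. For PHQ-9 above 10 the rule "will prompt the health coach to consider use of emotion regulation techniques to promote emotion regulation", and for LOCES above 25 it "will prompt the health coach to consider use of dialectic behavior therapy strategies to promote self-regulation". Where a low score is bad, the prompt fires on a low score. For the PASS: "A mean score <4 will prompt the health coach to utilize materials related to improving awareness of hunger and satiety cues". For diet and exercise self-efficacy: "A mean score < 4 on either subscale will prompt the health coach to access energy balance and self-efficacy treatment content".

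**The concern.** The printed cut-off does not fit the printed scale, and the inequality runs against the scale's anchors. If the battery is programmed as written, the score never produces a recommendation and nothing signals the failure. If someone repairs it by treating the score as a sum, the people reporting the least control over their emotions are the ones left out. In both cases the participants for whom the coping materials are meant are not picked up by this scale. What is at stake is the tailoring of visit content, not the analysis of weight.

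**Working it through.** **Inputs**, all from the Protocol's digital assessment section: 6 items; item range 1 to 10; 10 = most confident; trigger above 15, described as a mean. The documents give no derivation of 15, so there is nothing to reproduce beyond checking whether it can be attained.

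**As written (mean).**
- Lowest mean = (6 × 1)/6 = 1. Highest mean = (6 × 10)/6 = 10.
- 15 > 10, so no set of answers meets the rule.

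**Read as a sum.**
- Lowest sum = 6 × 1 = 6. Highest sum = 6 × 10 = 60. A cut-off of 15 is attainable.
- Equivalent item mean = 15/6 = 2.5.
- Part of the range above the cut-off = (60 − 15)/(60 − 6) = 45/54 = 83%. This describes the scale; it is not an estimate of how many participants would score there.
- A participant at 60 (fully confident) is flagged. A participant at 6 (no confidence on any item) is not.

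**Direction.** Higher means more confident, and the materials are for people who cope poorly, so the rule should fire on low scores. Changing mean to sum does not cure this; the inequality must also be reversed.

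**Is the fault general?** The same attainability check on the other triggers with a stated item range:

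| Scale | Items and range | Total range | Trigger | Attainable? |
|---|---|---|---|---|
| PHQ-9 | 9 items, 0–3 | 0–27 | >10 | Yes |
| LOCES | 7 items, 1–5 | 7–35 | >25 | Yes |
| UCLA Loneliness | 20 items, 1–4 | 20–80 | >40 | Yes |

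The numeric response ranges of the PASS, the diet and exercise scale and the social support scale are not given, so the attainability of their cut-offs cannot be checked. Their direction (low score prompts help) is sensible. Among the triggers that can be checked, the fault is confined to mental-health self-efficacy.

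**The case against.** The best reply is that this is a drafting slip with little reach. The cut-off actually programmed is not in the documents and may be correct. The rule prompts only consideration of materials. The PHQ-9 and LOCES prompts lead to overlapping content, so a distressed participant may be picked up another way. The exploratory analysis in the Protocol's statistical section and the SAP refers to mental-health self-efficacy itself and does not split participants at this cut-off. All of that stands and sets the severity. It does not rescue the printed rule, which a coach or programmer could not apply as intended.

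A reader might go further and infer that the battery will contaminate the control arm, because the PASS and diet and exercise prompts name no arm, both arms see a health coach, and both scales feed secondary outcomes. The documents do not support that inference:

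- None of the seven content prompts in the battery names an arm, so nothing singles out these two.
- The Aim 3 and randomization sections assign self-efficacy and psychophysical-awareness content to iOTA. Of the Health Education Control, the Protocol says "it does not teach self-efficacy or psychophysical awareness, and does not involve specific empirically supported psychotherapeutic techniques to help with weight management".
- The content of control visits is prescribed: "Visits will be structured according to current US Preventive Services Task Force recommendations to counsel participants on energy balance, physical activity and nutrition". Energy balance is therefore permitted there.
- Demonstrating fidelity of both conditions is a stated goal. Sessions are audio-recorded and reviewed by the investigators, and coaches rate their own delivery at each visit.

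Nor can the possible exposure be usefully bounded. The statistical section says psychophysical awareness is measured at every visit and gives a total of 5 time points, yet allows up to 10 visits for weight.

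**Conclusion.** The threshold is wrong as written: it cannot be reached as a mean, and it is reversed whether read as a mean or a sum. This rests only on the item count, range and anchors printed beside it, and needs no assumption about participants' scores. Severity is minor. The effect is on one route by which visit content is tailored. The plan for weight, BMI and the between-arm comparisons is unchanged. Whether any visit would be affected depends on the programmed rule matching the printed one, which the documents do not show.

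The lack of an arm label on the battery's prompts is a point for clarification, not an error, and is not evidence that control participants will receive iOTA content.

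**What to change.** Restate the trigger so that the materials are considered when the item mean, on the 1-to-10 scale, falls below a value the investigators fix before use. The documents do not supply that value. Reversing the printed figure as a sum (below 15, an item mean below 2.5) would be one candidate, but nothing in the text shows that it was intended. Then check the REDCap scoring rule against the corrected text.

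Optionally, add one sentence stating that all content prompts in the battery are acted on only as far as the assigned arm's content allows, alongside the existing fidelity monitoring.

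The cost is one corrected line, one programming check and, if wanted, one further sentence. No visits, measurements or participants are added.
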